Number of Subjects	37 (25 preeclamptic; 6 non-pregnant; 6 healthy, normotensive, pregnant)

Diagnosis and Main Inclusion/Exclusion Criteria
	
Diagnosis and Inclusion Criteria for women with severe preeclampsia
 
• Maternal age 18-45 years• Singleton or twin pregnancy with no known fetal anomalies• Early-onset preeclampsia defined as:
○ Early-onset: between 24 weeks 0 days and -33 weeks 3 days, based on menstrual dating confirmed by first or second trimester ultrasound OR second trimester ultrasound if menstrual dating unavailable;○ Preeclampsia:
▪ New onset hypertension and proteinuria, with systolic BP \geq 140 mm Hg and/or diastolic BP \geq 90 mm Hg on two occasions 6 hours apart and > 300 mg proteinuria on 24 hour urine collection OR urine P/C ratio >0.3;▪ New onset hypertension and NO proteinuria, with systolic BP \geq 140 mm Hg and/or diastolic BP \geq 90 mm Hg on two occasions 6 hours apart and one or more of the following: serum creatinine >1.1 mg/dL or doubling from baseline ,or central nervous system symptoms or visual changes▪ Severe gestational hypertension defined as new onset systolic BP \geq 160 mm Hg and/or diastolic BP \geq 105.○ Candidate for expectant management for at least 48 hours○ Deemed clinically stable by primary clinician and candidate for expectant management (delayed delivery) for at least 48 hours;• Maternal liver function tests < 2x ULN• Maternal platelet count \geq 100,000 mm³• Planned expectant management• Pre-existing medical diseases such as hypertension, diabetes, endocrine disorders, gastrointestinal diseases, are well controlled• Fetal well-being established by estimated fetal weight \geq 5th %tile; normal amniotic fluid volume (MVP \geq 2 cm); normal UA Dopplers; or reactive NST or BPP > 6• Delivery not anticipated within 48 hours of enrollment 
Exclusion Criteria for women with severe preeclampsia
 
• Pre-existing renal disease (creatinine \geq 1.5 mg/dL)• Any pre-existing medical condition that would increase risk for liver toxicity (e.g. hepatitis B or C; HIV; INH use)• Eclampsia; cerebral edema on CT/MRI; headache unrelieved by analgesics• Evidence of liver dysfunction (LFTs \geq 2x ULN)• Thrombocytopenia (platelets < 100,000 mm³)• Pulmonary edema• HELLP syndrome• Evidence of fetal compromise: EFW < 5th percentile; or BPP < 6; or absent or reverse diastolic UA blood flow; or oligohydramnios (MVP < 2 cm)

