Animal and laboratory data exist to support the theory of angiogenesis imbalance as the root cause of preeclampsia. Overexpression of sFlt-1 induces hypertension and fetal growth restriction in pregnant mice, and the time course of blood pressure increase mirrors the increase in sFlt-1.²² The preeclampsia-like clinical phenotype associated with sFlt-1 expression occurs via activation of the endothelin (ET) system.^{23, 24} In humans, low plasma vascular endothelial growth factor (VEGF) in the first trimester of pregnancy is a predictive marker for preeclampsia. In addition, sFlt-1/PlGF ratios are increased in women who subsequently develop preeclampsia compared to normotensive women.²⁵ ~90% of women with EOP have elevated sFlt-1.²⁶ An sFlt-1/PlGF ratio >0.85 is associated with adverse pregnancy outcomes: placental abruption, elevated liver enzymes and/or low platelets, and small-for-gestational-age birth weight and/or absent/reversed umbilical artery Doppler, and significantly shorter latency period, among women with EOP. 75% of women with sFlt-1/PlGF >0.85 deliver within one week and 85% within two weeks, compared to only 10% and 15% of women with sFlt-1/PlGF <0.85. sFlt-1/PlGF is a useful discriminator for women with EOP who are at risk for adverse outcome and need for delivery prior to 34 weeks.²⁷ The natural history of circulating sFlt-1 levels among women with preeclampsia has been described in several longitudinal studies.^{28, 29} sFlt-1 levels are elevated prior to the development of clinical symptoms of preeclampsia, and remain elevated until delivery.¹⁷ Based on this data, we believe that elevated circulating sFlt-1 levels identify those women at greatest risk for adverse outcome, particularly if managed expectantly, and thus the women most likely to yield benefit from treatments that allow for longer latency.

To address the angiogenic imbalance believed to be in the pathophysiology of preeclampsia, we²⁴ and others³⁰⁻³³ have demonstrated that ET receptor antagonists greatly ameliorate the preeclampsia-like phenotypes induced by sFlt-1 in animal models. While this data is promising, ET receptor antagonists are teratogenic and contraindicated in pregnant

[figure not shown]
[figure not shown]

Figure 1. Percent of medically indicated preterm birth (PTB) due to preeclampsia (PEX), fetal distress, small for gestational age (SGA), and abruption

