6.2 Study intervention and procedures for participants with early onset severe preeclampsia

The respective pharmacy will dispense vitamin B₃-amide, which will be administered given to the subject by study staff if out-patient or by in-patient nursing staff if in-patient. Study staff will meet with subjects at each prenatal visit or daily [(M-F) if in the hospital] to discuss compliance and side effects.

Clinical care will continue per recommendations of primary obstetrician caring for the patient. Standard procedures may include:

- 24-hr urine collection for protein excretion at admission
- Blood sampling for hematologic, liver, and kidney function at enrollment and every 2-3 days thereafter
- Physical examination by primary clinical provider
- Weight and intake/output measurement as ordered by primary clinical provider
- Magnesium sulfate for seizure prophylaxis
- Betamethasone to accelerate fetal lung maturity
- Antihypertensive agents
- Daily fetal surveillance by NST (30 minutes of continuous fetal heart rate monitoring) or BPP (30 minutes of ultrasound to monitor for fetal breathing, movement, fluid)
- Weekly ultrasound to measure amniotic fluid and UA Dopplers

The primary obstetrician will make decisions regarding indication and timing of delivery. Clinical management of the infant after delivery will be per standard treatment dictated by the neonatologist caring for the baby.

Study procedures include:

- Daily administration of vitamin B₃-amide, 2.5Gm given as administered as 1000mg at 8AM and 12MN; 500mg at 4PM
- Daily (if in-patient) or with each prenatal visit (if out-patient) study nurse visit to query side effects
- Optional blood sampling to coincide with clinical blood draws to measure nicotinamide and 2-pyridone, sFlt-1 and PIGF levels
- Optional blood sampling for Nicotinamide levels at the following times:
 - Day 1 - Baseline – pre 1st dose; Peak – 2 hrs post 1st dose; Trough – pre 2nd dose
 - Day 3 – Trough – pre AM dose; Peak – 2 hrs post AM dose
 - Day 7 - Trough – pre AM dose; Peak – 2 hrs post AM dose
 - Cord blood following delivery.
- Chart abstraction to review maternal liver function testing results, delivery data (up until discharge) and neonatal data (until 30 days of age or until discharge, whichever occurs

first)

6.2a Study intervention and procedures for healthy pregnant and non-pregnant controls

- Administration of a single dose (1000mg) of Nicotinamide at 8AM.

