- Blood sampling at baseline (pre-dose), 2 hours post dose, 8 hours post dose and 24 hours post dose.
- Urine sample at baseline (pre-dose), 8 hours post dose and 24 hours post dose.
- This will be done either in the clinic or the CTRC

6.3 **Laboratory specimen handling procedures**

Blood for research purposes will be collected at the time of clinically indicated blood draws. Specimens will be labeled with the subject's unique study ID and processed.

Specimens to be tested for circulating sFlt-1 and PlGF levels will be stored and shipped as a single batch on dry ice to the research laboratory at Harvard University. The interassay coefficient of variance for sFlt1 and PlGF immunoassays ranges from 2.6% to 3.0%.

Specimens collected for nicotinamide and 2-pyridone measurements will be sent to the UNC School of Pharmacy Lab ([name]). [name] developed a LC-MS/MS method using protein precipitation (acetonitrile) to measure nicotinamide and 2-pyridone during our previous phase I study.

7 **Statistical Plan**

7.1 **Statistical Methods**

Sample size: The study sample size was calculated to the primary outcome of MAP. We stipulated *a priori* that $\alpha = .05$ and $\beta = 0.2$. Using the highest BP measured within each 24-hr period and applying the following formula we will calculate daily MAP:

$$\text{mean arterial BP} = [2(\text{diastolic BP}) + \text{systolic BP}] \div 3$$

Assuming that the mean (\pm sd) MAP at enrollment of our subjects is 107 (\pm 10) mm Hg, to detect a difference from enrollment to 48 hours after treatment of 7 mm Hg in MAP requires that 20 subjects be enrolled. We will enroll 24 to allow for 20% attrition due to delivery prior to 48 hours of treatment.

- We will use a repeated measurement ANOVA to compare baseline MAP to MAP at 48 hours, 7 days and weekly thereafter until delivery or 34 weeks.
- Maternal liver toxicity: the proportion of women who develop elevated liver function tests (ALT and/or AST \geq 3x ULN within 24 hours of study drug) will be determined and compared to expected proportion of 20%.
- Descriptive report of proportion of women with
 - Side effects
 - Fetal effects

7.2 **Subject Population(s) for Analysis**

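### Delivery before 48 hours is handled only by enrolling more women; because delivery is tied to disease course, the before-after MAP change can be biased in either direction, and no analysis rule deals with this

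*Combined protocol and SAP*

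**What the plan says.** - **Sample size (Section 7.1).** The calculation is for one time point: "to detect a difference from enrollment to 48 hours after treatment of 7 mm Hg in MAP requires that 20 subjects be enrolled". Loss before that point is covered by recruitment: "We will enroll 24 to allow for 20% attrition due to delivery prior to 48 hours of treatment". No allowance is made for 7 days, which the Study Summary also names in the primary outcome.
- **Analysis (Section 7.1).** Repeated-measures ANOVA compares baseline MAP with MAP at 48 hours, 7 days and weekly until delivery or 34 weeks. MAP is built from the highest pressure in each 24-hour period: "applying the following formula we will calculate daily MAP". Nothing says what happens to a time point that falls after delivery.
- **Who is analysed.** Section 4.4.2 defines the full data set by at least 72 hours of supplementation and places the primary outcome at 72 hours. Section 7.2 includes every subject, even if untreated, without a method for missing MAP.
- **What delivery means (Sections 1.1 and 6.2).** The background says that preeclampsia resolves only with delivery and that indicated preterm birth follows fetal or maternal complications. Of women with an sFlt-1/PlGF ratio above 0.85, 75% "deliver within one week and 85% within two weeks"; with a lower ratio the figures are 10% and 15%. On who decides: "The primary obstetrician will make decisions regarding indication and timing of delivery".
- **Design (Section 3.1).** One open-label preeclampsia cohort. The 12 healthy women take a single dose for pharmacokinetics and are not a MAP comparator.

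**The concern.** Enrolling more women restores the number with a 48-hour MAP. It does not restore the mix. If those who deliver early differ in how their pressure was moving, the average change in those who remain differs from the average change in all women treated, at any sample size. A before-after comparison in one cohort has nothing against which such a shift would show.

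The two population rules make this worse. The 72-hour rule conditions the data set on staying undelivered past the time point for which the study is sized. The all-subjects rule points the other way but cannot be carried out as written. Classical repeated-measures ANOVA needs every time point, so adding the 7-day and weekly columns would narrow the sample further.

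MAP change is the trial's main efficacy result. Section 8 and Section 8.6 already treat delivery within 48 hours as an event to be notified to the FDA and the DSMB, yet the efficacy analysis treats it as plain attrition.

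**Working it through.** **Inputs from Section 7.1:** baseline MAP 107, SD 10; target change 7 mm Hg; alpha 0.05; power 80%; 20% delivered before 48 hours; n = 20, enrolled 24.

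**Assumptions:** a two-sided test; an SD of change of 10 (the plan gives only the SD at enrolment, and √[2(1-ρ)] × 10 = 10 when the repeat correlation ρ is 0.5); and the link r between delivery and MAP, which is not in the documents and is shown as a range.

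**1. The plan's own figure.** Paired t test, 7/10 = 0.7 SD: 19 women give 82.3% power and 20 give 84.4%. The stated 20 is reproduced within one woman. For attrition, 20 × 1.2 = 24, which leaves 24 × 0.8 = 19.2 women; 20/(1-0.2) = 25, the figure in the Study Summary. The numbers are adequate. The issue is which women remain.

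**2. Delivery follows a rise in MAP, no drug effect.** Let a fraction p deliver, chosen by a normal variable with correlation r to the MAP change. The mean change in those remaining is

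-r × 10 × φ(z)/(1-p), where z is the (1-p) normal quantile.

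For p = 0.20: z = 0.842, φ = 0.280, 0.280/0.80 = 0.350, so the change is -3.5r. The false-fall rates come from simulated trials with 24 or 25 women and a one-sample t test on those remaining, against a nominal 2.5% in the lower tail.

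| r | Apparent 48-hour change (mm Hg) | False significant fall |
|---|---|---|
| 0 | 0 | 2.5% |
| 0.3 | -1.05 | 6% to 7% |
| 0.5 | -1.75 | 12% |
| 0.7 | -2.45 | 20% to 21% |
| 1 (limit) | -3.5 | 46% |

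**3. Delivery follows baseline MAP instead.** Women with high baselines leave, and they are the ones expected to regress downward. The slope of change on baseline is -(1-ρ), so those remaining show +(1-ρ) × r × 3.5. With ρ = 0.5: r = 0.3 gives 0.5 × 0.3 × 3.5 = +0.5; r = 0.7 gives +1.2; r = 1 gives +1.75 mm Hg. The bias changes sign.

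**4. Seven days.** The documents give no 7-day delivery rate for eligible women. Two values bracket an assumption: 50%, and 68.5%. The latter is 0.9 × 75% + 0.1 × 10%, which treats the roughly 90% with raised sFlt-1 in Section 1.1 as if all had a high ratio. The multipliers are 0.399/0.50 = 0.798 and 0.355/0.315 = 1.128.

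| Delivered by 7 days | r = 0.3 | r = 0.5 | r = 0.7 | Women left of 24 |
|---|---|---|---|---|
| 50% | -2.4 | -4.0 | -5.6 | 12 |
| 68.5% | -3.4 | -5.6 | -7.9 | about 7.5 |

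False falls are about 12%, 28% and 56% to 58% in the first row, and 13%, 31% to 33% and 61% to 64% in the second.

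**The case against.** The other side has good points, and most of them limit the claim.

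- **MAP will appear to fall.** A reader might infer this. The documents do not support it: no section gives a pressure criterion for delivery, Section 1.1 names fetal as well as maternal complications, Section 4.4.1 refers to delivery for fetal reasons, and antihypertensives given as needed (Section 5.5) loosen any link. The link may be near zero, and step 3 shows that the sign can reverse.
- **The plan drops women who deliver.** No section says so outright. Section 7.2 says the opposite. The defect is a contradiction with Section 4.4.2 and the absence of a method.
- **The protocol implies that 68.5% deliver by 7 days.** It does not. Raised sFlt-1 and a ratio above 0.85 are different markers. Eligibility also excludes HELLP, low platelets, liver dysfunction, fetal compromise and delivery expected within 48 hours, and it admits severe gestational hypertension.
- **Selection could explain the whole 48-hour target.** It cannot under these assumptions: the limit is 3.5 of 7 mm Hg.
- **The information is already collected.** Delivery data are abstracted and early deliveries are notified. That is true, and it makes the fix cheap, but monitoring does not correct an estimate.

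What remains is that no rule links delivery to the MAP analysis, and the bias, in whichever direction, cannot be seen in a single cohort.

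**Conclusion.** The point holds in a conditional form. The plan makes up for delivery by enrolment, conditions one data set on 72 hours of treatment, and gives no method for a missing 48-hour MAP, although its own background makes delivery prognostic. The MAP change can therefore be biased toward a fall if delivery follows rising pressure, or toward a rise if it follows baseline pressure.

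At 48 hours the size is modest: about 1 to 2.5 mm Hg downward or 0.5 to 1.2 upward over the assumed links. This is enough to raise the false-fall rate from 2.5% to between 6% and 21% in the downward case. At 7 days it may approach or pass 7 mm Hg, but only under an assumed delivery rate. All sizes rest on an SD of change of 10 and on link strengths that the documents do not give. Severity: should-fix.

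**What to change.** 1. **Section 7.1:** replace the repeated-measures ANOVA with a likelihood-based repeated-measures mixed model in all dosed women, using every daily MAP recorded before delivery and leaving out readings in labour. Keep the 48-hour change as the main contrast.
2. **Sections 4.4.2 and 7.2:** remove the 72-hour restriction for the MAP analysis, state one analysis set, and reconcile the 72-hour wording with the 48-hour time point.
3. **Sensitivity analyses, prespecified:** undelivered women only; delta-adjusted values for women delivered before the time point; and the last completed pre-delivery 24-hour MAP. The last should not be the main analysis. It can reverse the bias (up to about +1.0 mm Hg), and it does little for a woman who delivers before completing a post-dose 24-hour period.
4. **Reporting:** beside each MAP result, give the number delivered by 48 hours and by 7 days, with the indication.

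The cost is SAP wording and a little more analysis. Daily MAP and delivery data are already planned, although women sent home are typically seen about twice a week (Section 3.1), so some days will have no reading; the model accepts this. Its limit should be stated: it removes the bias only when delivery depends on MAP already observed, and otherwise corrects it in part. The sensitivity analyses and a cautious conclusion at 7 days are still needed.

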
Statistical Methodology
	
Primary Outcome
 
• Mean arterial blood pressure before, 48 hours, and 7 days after daily dosing 
Secondary Outcomes
 
• Maternal liver toxicity: the proportion of women who develop elevated liver function tests (ALT and/or AST \geq 3x ULN within 24 hours of study drug) will be determined and compared to expected proportion of 20%• Maternal side effects (nausea, vomiting, rash, headache)• Optional: Plasma nicotinamide and 2-pyridone levels; sFlt-1 and PIGF levels

1. Introduction

This document is a protocol for a human research study. This study is to be conducted according to US and international standards of Good Clinical Practice (FDA Title 21 part 312 and International Conference on Harmonization guidelines), applicable government regulations and Institutional research policies and procedures.

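### Section 7.1 sizes one MAP comparison but tests several against baseline with no order, gate or adjustment, so control of the error rate at .05 is not secured

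*Combined protocol and SAP*

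**What the plan says.** Section 7.1 ties the sample size to one outcome ("The study sample size was calculated to the primary outcome of MAP"), with one alpha of .05 and beta of 0.2. The sizing sentence concerns a single contrast: "to detect a difference from enrollment to 48 hours after treatment of 7 mm Hg in MAP requires that 20 subjects be enrolled". The allowance for losses is tied to the same time: "We will enroll 24 to allow for 20% attrition due to delivery prior to 48 hours of treatment".

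The analysis sentence that follows lists more comparisons: "We will use a repeated measurement ANOVA to compare baseline MAP to MAP at 48 hours, 7 days and weekly thereafter until delivery". The other limit it sets is 34 weeks. It gives no order, no adjustment, no rule that later tests depend on earlier ones or on an overall test, and no sidedness.

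The sections do not agree on the primary time:

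- Study Summary, Objectives: effect on MAP at 48 hours and at 7 days.
- Study Summary, Statistical Methodology, primary outcome: "Mean arterial blood pressure before, 48 hours, and 7 days after daily dosing". Neither time is ranked first.
- Section 3.2: MAP as the highest value in a 24-hour period, with no time point.
- Section 4.4.2: primary outcome measured at 72 hours, a time that appears in neither the sizing nor the analysis sentence.

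**The concern.** The trial has one treated arm with preeclampsia, so the change from baseline carries the whole efficacy claim. The plan set a formal alpha and a powered test for that claim, but a reader cannot tell which comparison is the test. A result that is significant at 7 days and not at 48 hours, or only at a later week, could be reported as a positive primary outcome under the present text. The more times that can carry the claim, the further the chance of a false one moves from the figure stipulated. With the primary time left open, the choice could also be made after the data are seen.

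**Working it through.** **Inputs.** From section 7.1: alpha .05, beta 0.2, difference 7 mm Hg, SD 10 mm Hg (given for MAP at enrollment), 20 women. Assumed, because the documents do not say: two-sided tests, and a within-woman correlation of 0.5. With that correlation the SD of the change is 10 × √(2 × (1 − 0.5)) = 10.

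**1. The plan's own figure.** For a paired comparison, n = [SD × (z for alpha + z for power) / difference]² = [10 × (1.960 + 0.842) / 7]² = 16.02, so 17. With the t distribution it is 18.03, so 19. The stated 20 fits a two-sided paired test of one contrast and has 84% power. A one-sided t test would need only 15. The sizing thus supports one two-sided test at 48 hours.

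**2. How many comparisons.** The Study Summary gives two (48 hours, 7 days). If measurement stops with the two-week treatment limit in 4.4.1, there are three (48 hours, day 7, day 14). Sections 5.2 and 8.4 run treatment to delivery or 34 weeks instead. Those passages conflict and must be reconciled; the count depends on them.

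**3. Error if the tests were independent.** 1 − 0.95² = 0.0975 for two times; 1 − 0.95³ = 0.143 for three.

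**4. Error with the shared baseline.** Every contrast subtracts the same baseline. Under compound symmetry with correlation ρ and unit variance, two changes have covariance 1 − ρ and variance 2(1 − ρ). Their correlation is therefore 0.5 whatever ρ is. Simulated null trials (20 women, complete data, paired t tests at two-sided .05; compound symmetry, or correlation decaying by 0.5 or 0.8 per week) gave:

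| Times tested | At least one false change | At least one false fall |
|---|---|---|
| 48 h only | 5% | 2.5% |
| 48 h + 7 days | 9.1–9.3% | 4.6–4.7% |
| 48 h + 7 days + 14 days | 12.4–13% | 6.3–6.6% |

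**5. Reading the ANOVA as one overall F test.** For two or three follow-up times the simulated error is about 0.05 under compound symmetry. When correlation decays with time and no sphericity correction is made (none is specified), it is 0.061–0.065 for two times and 0.068–0.075 for three. A significant F shows some difference among times. It does not show a fall at 48 hours.

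**6. Cost of the possible remedies.** With 48 hours as the single primary test, or first in a fixed sequence, alpha stays .05, n stays 20 and power stays 84%. Bonferroni over two times needs 22 evaluable women for 80% power, and power at 20 falls to 75%. Over three times it needs 25, and power at 20 falls to 69%.

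**The case against.** The strongest defence is that 48 hours is already primary by implication: it is the only contrast that was sized, and the attrition allowance refers to it. Taken alone, section 7.1 could be read that way, and alpha would then hold. But the Study Summary puts 7 days beside it, 3.2 gives no time and 4.4.2 says 72 hours, so the implication does not settle the matter.

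A second defence is that the named method is a repeated-measures ANOVA, not a set of paired t tests. This stands in part. One overall F test keeps about 5% under compound symmetry, so it would be too strong to say that alpha is not held; the text is ambiguous. It describes comparisons with baseline, however, and does not make them conditional on an overall test. Likewise, requiring success at both 48 hours and 7 days would not inflate the error, but no section says so.

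Four stronger readings are tempting and are not supported:

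- **That the chance of falsely claiming a fall is about double 5%.** The 9% counts rises as well as falls. For falls alone, two times give 4.6–4.7%: nearly double the 2.5% of one two-sided test, but still below .05.
- **That the error is about 30%.** Entry at 24 weeks 0 days and follow-up to 34 weeks allow 48 hours plus ten weekly values, and eleven tests give 26–32%. That needs every woman to enter at the earliest date and stay undelivered for ten weeks. Entry runs to 33 weeks 3 days, and a woman entering then reaches 34 weeks in four days, without a 7-day value.
- **That missing late visits make such figures upper limits.** For a fixed number of tests the reverse holds. With four times and illustrative random losses to 20, 10, 5 and 3 women, the error rose from about 0.16 to about 0.18. It falls only if some tests cannot be run.
- **That the shared baseline makes matters worse.** Sharing lowers the family-wise error slightly (0.092 against 0.0975), and a chance-high baseline would affect a 48-hour test alone just as much.

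Finally, this is a small, open-label phase II study, which limits the weight of the point.

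**Conclusion.** The concern holds in this form: the plan stipulates one alpha and sizes one contrast, lists several comparisons without order, gate or adjustment, and contradicts itself on the primary time. Control at .05 is not secured. It is not shown to fail under every reading.

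If each contrast is tested at two-sided .05, the chance of at least one false change is about 9% for 48 hours plus 7 days and about 13% for three times. For false falls only it is about 4.7% and 6.6%, against 2.5% for one test. These figures rest on 20 women with complete data, two-sided testing, and either compound symmetry (0.5) or the decaying correlations tried. The point should be corrected, but it does not by itself invalidate the study.

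**What to change.** In the Study Summary, 3.2, 4.4.2 and 7.1, use the same statement of the primary analysis:

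- The single primary test is the change in MAP from baseline to 48 hours, at two-sided .05, estimated as a within-woman contrast from the repeated-measures model.
- The 7-day change is tested at two-sided .05 only if the 48-hour test is significant.
- Later weeks are reported as estimates with confidence intervals and no claim of significance.
- The 72-hour statement in 4.4.2, including its use in defining the full data set, is reconciled with this.

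The cost is wording. The stated 20 women do not change. The downside is that 7 days can no longer carry the primary claim on its own. If the sponsor wants it to, naming both times as primary with an adjustment is also valid. With Bonferroni over two times, 48-hour power at 20 women falls from 84% to 75% (SD of change 10 assumed), or 22 evaluable women are needed for 80%.
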